### 2.2.1.2. Key Secondary Efficacy Endpoints

Four key (alpha-protected) secondary outcomes have been selected for which formal hypothesis testing will be conducted. A fixed-sequence approach to controlling the type I error rate will be used. First, the primary endpoint above will be tested, followed by the four key secondary endpoints in the sequence with which they are presented below.

The efficacy of varespladib plus SOC vs. SOC alone will be assessed for these four outcomes. Details of this approach are described in [section 8.1.2](#).

- Area under the curve (AUC) of the pulmonary, cardiovascular, local wound, hematologic symptoms, renal, and nervous system sections of the SSS from baseline through Day 7
- Total antivenom administration in vials from Baseline through Day 28
- AUC of the Numeric Pain Rating Score (NPRS) from baseline through Day 3
- Clinical Global Impression-Improvement (CGI-I) scale at Day 2

### 2.2.1.3. Other Secondary Endpoints

The study has the following other secondary efficacy endpoints:

- Complete SSS from baseline (pre-dosing) through Day 7
- SSS neurologic system subscore from Baseline through Day 3
- Coagulation abnormalities from Baseline through Day 7
- Hemolysis markers from baseline through Day 3
- Levels of the myonecrosis marker, creatinine kinase (CK), from Baseline through Day 3
- Numeric Pain Rating Scale (NPRS) score in subjects able to respond from Baseline through Day 28
- Kidney function markers from baseline through Day 28
- Head-Lift duration from Baseline through Day 7
- Total duration of ventilatory support from Baseline through Day 28
- Total duration of Intensive Care Unit (ICU) stay from Baseline through Day 28
- Total duration of hospitalization from Baseline through Day 28
- All-cause mortality from Baseline through Day 28
- CGI-I scale from Baseline through Day 7
- PGIC from Baseline through Day 7
- Patient-Specific Functional Scale (PSFS) total score from Baseline through Day 28

## 2.2.2. Safety and Tolerability Endpoints

The study has the following safety and tolerability endpoints:

- Incidence and severity of adverse events (AEs), serious AEs (SAEs), and AEs leading to discontinuation of Investigational Product (IP)
- Safety of varespladib-methyl as assessed by the number and rates of reported treatment-

emergent adverse events (TEAEs) from beginning of treatment until last Follow-Up Visit/Phone call at Day 28

- Treatment-related SAE from beginning of treatment until last Follow-up Visit/Phone call at Day 28
- Safety as assessed by
  - Vital signs
  - Clinical laboratory evaluations: complete blood count (CBC), urinalysis, liver function tests (LFTs), renal function tests (albumin, creatinine, blood urea nitrogen [BUN], estimated glomerular filtration rate [eGFR])
  - 12-lead electrocardiogram (ECG)
- Concomitant medications and therapies
- Columbia-Suicide Severity Rating Scale (C-SSRS) evaluated at Baseline or at the earliest time point clinically allowable (ideally Day 1) and then at every study visit through Day 28

Safety endpoints will be analyzed according to the following FDA Medical Queries (FMQs):

- Hepatic Injury (Narrow and Broad)
- Acute Kidney Injury (Narrow and Broad)
- Stroke and Transient Ischemic Attack [TIA] (Narrow and Broad)
- Myocardial Ischemia (Narrow)
- Arrhythmia (Narrow)
- Cardiac Conduction Disturbance (Narrow)
- Hypersensitivity (Standard Narrow and Broad)

### **2.2.3. Pharmacokinetics**

PK parameters of varespladib-methyl in plasma from a subset of adult and pediatric subjects at specified timepoints on Days 1 and 3 and from all subjects pre-dose on Day 7.

### **2.2.4. Exploratory Endpoints**

The exploratory efficacy endpoints of this study include the following:

- Change in the SSS from Baseline through Day 7 using a compressed SSS scale.
- SSS from Baseline through Day 28
- Grip strength pre-dosing through Day 28
- SSS neurologic system subscore from Baseline through Day 7
- Analgesic use from Baseline through Day 28
- CGI-I from Baseline through Day 28
- PGIC from Baseline through Day 28
- CBC through all SSS evaluation days
- Transfusion requirement from Baseline through Day 28

- CRP from Baseline through Day 14
- D-dimer levels from Baseline through Day 14
- Levels of myonecrosis marker (CK) from Baseline through Day 3 in subjects presenting with and without tourniquets at enrollment
- Secretory phospholipase A2 (sPLA2) in serum at specified timepoints on Days 1 to 7 in all subjects

### **3. Overall Study Design and Plan**

#### **3.1. Overall Design**

This is a multi-center, randomized, double-blind, placebo-controlled, phase 2 study designed to evaluate the safety, tolerability, and efficacy of varespladib-methyl, concurrently with SOC, in subjects bitten by venomous snakes. Subjects who have experienced a venomous snakebite with evidence of snakebite venom toxicity (see Study Population, [Section 3.3](#), below) and who meet other inclusion criteria will be eligible for participation in the study. Consenting participants will be enrolled and randomized to receive study drug (active varespladib-methyl or placebo) in a 1:1 ratio. Study drug will be taken twice a day for a period of 7 days. Subjects in both arms of the trial will receive SOC. Outcomes will be assessed over a follow-up period of 28 days.

#### **3.2. Sample Size and Power**

The sample size for this phase 2 study was determined by a formal power calculation based on the primary efficacy endpoint. This study was powered at 85% to detect a statistically significant (2-sided alpha = 0.05) treatment effect. The assumptions are the following:

- 2-sided alpha level 5%
- Power 85%
- Randomization ratio 1:1
- A minimum difference in the change from Baseline to the average at 6- and 9-hour pulmonary, cardiovascular, hematologic, renal, and nervous system subscores of the SSS of 1.1 points and a standard deviation 1.75

A sample size of 94 patients will provide 85% power to identify a difference of 1.1 in the primary outcome (two-sided alpha = 0.05). The sample size has been calculated using nQuery 8.

The randomization scheme will be 1:1 stratified by age group (5 to < 11, 11 to < 18, and  $\geq$  18 years old) and by the presence or absence of neurotoxicity (SSS nervous system subscore of 0–1 or  $\geq$  2) at Baseline, resulting in 6 strata in total.

Because we anticipate up to 15% withdrawal through the end of the study, we requested permission to enroll up to 110 patients to ensure adequate power for secondary outcomes.

#### **3.3. Study Population**

The study population comprises subjects of both genders, aged  $\geq$  5 years, with venomous snakebite. The index event (snakebite) must be symptomatic and symptom onset must have

occurred within 10 hours of eligibility assessment and the subject must be willing (or legally authorized representative is willing) to provide informed consent prior to initiation of any study procedures.

Subjects must meet one of two categories of inclusion criteria:

1. Subjects who *have not yet* completed their initial dose of antivenom may be eligible if they have an SSS inclusion criteria score (excludes GI and renal subscores) of  $\geq 3$  points in any single SSS category or a score of 2 in one category and at least 1 in any other category.
2. Subjects who *have* completed their initial dose of antivenom may be eligible if they have an SSS inclusion criteria score (excludes GI and renal subscores) of  $\geq 2$  points.

### **3.4. Treatments Administered**

Varespladib-methyl or placebo will be administered, concurrently with institutional SOC, to subjects with suspected or confirmed snakebite envenoming:

- Adult subjects will receive an initial loading dose of 500 mg ( $2 \times 250$  mg oral tablet) varespladib-methyl upon randomization, followed by dosing with 250 mg varespladib-methyl ( $1 \times 250$  mg oral tablet) approximately 12 hours later, and subsequent BID dosing with  $1 \times 250$  mg varespladib-methyl oral tablets for the remainder of the 7-day treatment period. Tablets may be administered via feeding tube (e.g., naso- or orogastric tubes) in subjects requiring mechanical ventilation.
- Pediatric subjects (ages 5 to  $< 18$ ) will be administered doses of varespladib-methyl determined by allometric scaling, provided as 50 mg capsules. Age-appropriate capsules, as described in [Section 7.3](#) of the protocol, may be administered via feeding tube (e.g., naso- or orogastric tubes) in subjects requiring mechanical ventilation.
- The timing of initial snakebite envenoming, and administration of SOC will be considered when determining study subject eligibility.

### **3.5. Method of Assigning Subjects to Treatment Groups**

In this parallel-group randomized study, subjects who meet study entry criteria will be randomly assigned in a 1:1 ratio to varespladib-methyl or placebo. The randomization schedule, which will be computer generated using a permuted block algorithm, will randomly allocate IP to randomization numbers. The randomization numbers will be assigned sequentially through a central interactive web response system (IWRS) as subjects are entered into the study. The randomization schedule will be stratified by age group (5 to  $< 11$  years, 11 to  $< 18$  years, and  $\geq 18$  years) and by the presence or absence of moderate to severe neurotoxicity (SSS nervous system subscore of 0–1 or  $\geq 2$ ) at Baseline, resulting in 6 strata in total. Study center will not be a blocking factor in the randomization schedule. The block sizes will not be divulged to the Sponsor or the investigative team. No one involved in the study performance will have access to the randomization schedule before official unblinding of treatment assignment. The

randomization schedule will be prepared by the clinical research organization (CRO) before the start of the study. No subject will be randomized into this study more than once.

A subject will be considered randomized when the IWRS has given the treatment number to be allocated.

### **3.6. Blinding and Unblinding**

All subjects, investigators, and study personnel involved in the conduct of the study, including data management, will be blinded to treatment assignment except for a specified unblinded statistician and programmer from the study CRO who will have access to the randomization code. The unblinded study personnel will not participate in study procedures or data analysis prior to unblinding of the study data to all study-related personnel upon database lock. If an interim analysis is conducted, then unblinded personnel who are not otherwise involved in the study will prepare the data for review.

Study personnel will make every effort to safeguard the integrity of the study blind to minimize bias in the conduct of the study. Treatment unblinding is discouraged if knowledge of the treatment assignment will not materially change the planned management of a medical emergency. Unblinding will be permitted in a medical emergency that requires immediate knowledge of the subject's treatment assignment.

Unblinding should be discussed in advance with the medical monitor, if possible. For emergency unblinding, study personnel will use the IWRS. If the Investigator is not able to discuss treatment unblinding in advance, they must notify the medical monitor as soon as possible about the unblinding incident without revealing the subject's treatment assignment.

Unblinding for an individual subject will not result in unblinding the treatment assignments for the remaining subjects in the study. Thus, the overall study blind will not be compromised.

### **3.7. Schedule of Events**

Please see [Table 1](#) of the protocol for a detailed schedule of events.

## **4. Statistical Analysis and Reporting**

### **4.1. Introduction**

Data processing, tabulation of descriptive statistics, calculation of inferential statistics, and graphical representations will primarily use SAS (release 9.4 or higher). If the use of other software is warranted, the final statistical methodology report will detail what software was used for what purposes.

Continuous (quantitative) variable summaries will include the number of subjects (n) with non-missing values, mean, standard deviation, median, 25th percentile, 75th percentile, minimum, and maximum.

Categorical (qualitative) variable summaries will include the frequency and percentage of

subjects who are in the particular category or each possible value. In general, the denominator for the percentage calculation will be based upon the total number of subjects in the study population for the treatment groups, unless otherwise specified.

The minimum and maximum will be reported with the same degree of precision (i.e., the same number of decimal places) as the observed data. Means will be reported to 1 degree of precision more than the observed data and measures of spread will be reported to 2 degrees of precision more than the observed data. Medians will be reported to the degree of precision measured.

Percentages will be presented to 1 decimal place, unless otherwise specified.

Unless otherwise indicated, all statistical tests will be conducted at the 0.05 significance level using 2-tailed tests, and *P* values will be reported. Corresponding 95% confidence intervals (CIs) will be presented for statistical tests.

This study is considered a confirmatory study. Statistical tests will be regarded as formal tests of specific hypotheses.

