## 8. Efficacy Analysis

### 8.1. Primary Efficacy Analysis

#### 8.1.1. Primary Efficacy Endpoint

The primary efficacy endpoint is the change in the composite outcome of the pulmonary, cardiovascular, hematologic, renal, and nervous system sections of the snakebite severity score (SSS) from Baseline (pre-dosing) to the average of the scores from 6 and 9 hours after first dose: Change = (Baseline - [6hr + 9hr]/2).

The ITT population will be used to analyze the primary efficacy endpoint. For completeness the analyses will be repeated for the PP population.

Descriptive statistics for the SSS as well as the 6hr and 9hr mean scores will be tabulated by treatment group.

The primary analysis will use ANCOVA. A sensitivity analysis will use rank-regression applying the same adjustment covariates as specified in the ANCOVA. To better understand the appropriateness of applying a parametric vs. nonparametric approach, the CSR will include diagnostics plots of ANCOVA residuals.

The change from baseline to the average of the 6hr and 9hr scores will be compared between treatment groups using an ANCOVA with the baseline SSS score, subject age group, the presence or absence of baseline neurotoxic symptoms, and country as covariates. The varespladib-methyl to placebo (varespladib-methyl vs. placebo) will be compared at the 5% two-sided significance level; corresponding 95% two-sided confidence interval for the difference will be presented.

Six sets of subgroup analyses will be performed: (1) patient age, (2) baseline neurotoxic symptoms, (3) prior receipt of antivenom, (4) country, (5) snake type, and (6) timing of receipt of study drug. The following paragraphs describe these six sets of subgroup analyses.

1. *Patient age.* Summary statistics, including baseline SSS and least square means from the ANCOVA, will be presented separately for pediatric (5 to 17 years) and adult ( $\geq 18$  years) subjects. If the study includes too few children to fit an ANCOVA, only summary statistics will be presented.

2. *Baseline neurotoxic symptoms.* The treatment effect will be estimated in subjects with and without moderate or severe neurotoxic symptoms at baseline (SSS nervous system score of 0-1 vs. 2-3). These analyses will be analogous to those described for the pediatric and adult subgroup analyses, except that the ANCOVA will include age group, but not neurotoxicity.

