### 8.1.2. Key Secondary Efficacy Endpoints

The ITT population will be used to analyze the secondary efficacy endpoints. All secondary endpoints will be analyzed using the prespecified assessment timepoints according to the protocol. All statistical models for change from baseline in a particular endpoint will include covariates for baseline value of the particular endpoint, baseline SSS, baseline neurotoxicity (Yes, No; based on the SSS neurological system subscore), age group (5-17, 18+), and country (U.S. vs. India). Key secondary endpoints will be tested sequentially using a fixed-sequence gatekeeping procedure for the hierarchical testing of multiple endpoints. The significance of the treatment effect for the primary endpoint (i.e., change in SSS from baseline to average at 6 and 9 hours) will be the first hypothesis tested, using a significance level of 0.05. If the null hypothesis for the primary endpoint is rejected, then the first key secondary endpoint (i.e., AUC of SSS through Day 7) will be tested, also with a significance level of 0.05. If the null hypothesis for this test is rejected, the second key secondary endpoint (total antivenom use) will be tested ( $\alpha=0.05$ ).

If the null hypothesis for this test is rejected, the third key secondary endpoint (AUC of NPRS through Day 3) will be tested ( $\alpha=0.05$ ). If the null hypothesis for this test is rejected, the fourth key secondary endpoint (CGI-I at Day 2) will be tested ( $\alpha=0.05$ ). Sensitivity and subgroups analyses of the primary and key secondary endpoints will not be part of the gatekeeping procedure for hierarchical testing of endpoints.

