## 8.2. Other Secondary Efficacy Analyses

The other secondary efficacy analyses will be interpreted as exploratory analyses. All secondary endpoints will be analyzed according to the prespecified assessment timepoints listed in the protocol. Statistical models will include covariates for baseline SSS, baseline neurotoxicity (Yes, No; based on the SSS neurological system subscore), age group (5-17, 18+), and, when available, the baseline value of the particular endpoint unless otherwise specified below. A sensitivity analysis will include as a covariate yes/no completion of an initial dose of antivenom prior to randomization. The methods described here are what is currently planned. However, for each analysis, we will examine the distribution of the strata pooled over treatment and placebo. If the data are unlikely to support the planned analysis or if the model fails to converge, removal of covariates and different estimation routines will be attempted and described in the CSR.

### 8.2.1. Complete SSS from Baseline through Day 7

The complete SSS (all sub-sections including pulmonary, cardiovascular, hematologic, renal, nervous system, gastrointestinal, and local wound) from baseline through Day 7 after first dose will be summarized using descriptive statistics of observed values and changes from baseline.

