## **8.4. Subgroup Analyses of Efficacy Variables**

The primary efficacy endpoint and the three key secondary efficacy endpoints will be analyzed by doing separate subgroup analyses for the following subgroups: (1) pediatric (age 5 to 17 years) and adult ( $\geq 18$  years) subgroups, (2) among subjects with and without neurotoxic symptoms at baseline as described in [section 8.1](#), (3) among subjects who did and did not complete an initial dose of antivenom prior to randomization, (4) among subjects enrolled in the U.S. and India, (5) among patients bitten by vipers, elapids, and unknown snake types, and (6) among patients for whom the time from bite or symptom onset to receipt of study drug was  $< 5$  hours and  $\geq 5$  hours.

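### SAP 4.1 does not confine formal testing to the five fixed-sequence hypotheses, and the subgroup analyses have neither an exploratory label nor an interaction test

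*SAP*

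**What the plan says.** SAP 4.1 sets the general rule: "Unless otherwise indicated, all statistical tests will be conducted at the 0.05 significance level using 2-tailed tests", with P values reported. It closes with: "This study is considered a confirmatory study. Statistical tests will be regarded as formal tests of specific hypotheses". No list of hypotheses is attached to that sentence.

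Other sections are narrower. SAP 2.2.1.2 says: "Four key (alpha-protected) secondary outcomes have been selected for which formal hypothesis testing will be conducted", to be tested after the primary endpoint. SAP 8.2 says: "The other secondary efficacy analyses will be interpreted as exploratory analyses".

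For subgroups, SAP 8.1.1 says: "Six sets of subgroup analyses will be performed". The factors are age, baseline neurotoxicity, prior antivenom, country, snake type and time to study drug. SAP 8.1.2.1 to 8.1.2.4 repeat the six factors for each key secondary endpoint. SAP 8.4 says the endpoints "will be analyzed by doing separate subgroup analyses for the following subgroups", but counts three key secondary endpoints where 2.2.1.2 and 8.1.2 have four.

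On the status of these analyses the SAP says only: "Sensitivity and subgroups analyses of the primary and key secondary endpoints will not be part of the gatekeeping procedure for hierarchical testing of endpoints" (in 8.1.1 and again in 8.1.2). The only interactions specified anywhere are with time or visit, in the repeated-measures models.

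**The concern.** Taking subgroups out of the gatekeeping says that they carry no protected alpha. It does not say how their P values are to be read. The SAP does use the word exploratory elsewhere: for the other secondary analyses, for the collapsed antivenom model in 8.1.2.2, and for all of 8.3. It does not use it for subgroups, so the general sentence in 4.1 is the only text left that describes them.

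The analysis method adds to this. With a separate model in each level and no interaction term, a reader who asks whether the drug works differently in the U.S. and India, or in viper and elapid bites, can only compare results from strata of about 94 patients in total. Two wrong conclusions are then possible. A trial that misses its primary endpoint could present a nominally significant subgroup as a pre-specified result. A trial with one uniform effect could be read as showing benefit in some subgroups only.

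**Working it through.** **Plan's own figure.** The inputs in SAP 3.2 are a difference of 1.1, SD 1.75, two-sided 0.05, 85% power and 1:1 allocation. The normal approximation gives n per arm = 2 × (1.960 + 1.036)² × (1.75/1.1)² = 2 × 8.98 × 2.531 = 45.4, so 46. The exact t-test needs 47 per arm (power 85.4%), which is 94 in total. The plan's 94 is reproduced and is used below.

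**Count.** Levels: age 2 + neurotoxicity 2 + prior antivenom 2 + country 2 + snake type 3 + timing 2 = 13. Five endpoints give 13 × 5 = 65. With the count in 8.4 it is 13 × 4 = 52. It is lower still if pediatric models are not fitted, which 8.1.1 allows for the primary endpoint.

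**No true effect.** If each level yields a P value at 0.05, the expected number of false positives among 65 is 65 × 0.05 = 3.25. Under independence, the chance of at least one is 1 − 0.95¹³ = 48.7% for the primary endpoint and 1 − 0.95⁶⁵ = 96.4% for all five. Independence is wrong because every factor re-splits the same patients, so the figures below come from simulation.

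The simulation used N = 94, t-tests within levels, independent factors and an endpoint correlation of 0.5. The assumed shares were age 15/85, neurotoxicity 20/80, prior antivenom 40/60, country 50/50, snake type 60/15/25 and timing 50/50. The documents give neither the shares nor the correlation.

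| Result under no effect | Share of trials |
|---|---|
| Any P<0.05 among 13 primary-endpoint subgroups | about 35% |
| Favourable primary-endpoint subgroup with overall test non-significant | about 16% |
| Any P<0.05 among 65, either direction | about 82% |
| Any favourable P<0.05 among 65 | about 51% |

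Two other sets of shares, with correlations from 0 to 0.9, gave 33% to 37% for the first row, 57% to 89% for the third and 32% to 64% for the fourth.

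**Uniform effect of 1.1/1.75 in everyone.** Take one 50/50 factor, with 47 patients per level and 23.5 per arm. The SE is 1.75 × √(2/23.5) = 0.511, and 1.1/0.511 = 2.15. Power in each half is therefore Φ(2.15 − 1.96), about 58%. The chance that one half is significant and the other is not is 2 × 0.577 × 0.423 = 49%. Over all six factors and the assumed shares, the simulation gives at least one such discordant factor in about 94% of trials, on average about 3.5 of the six.

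**What an interaction test can do.** Take a 50/50 split with the full 1.1 points in one half and none in the other. The SE of the interaction is 1.75 × √(4/23.5) = 0.722, and 1.1/0.722 = 1.52. Power is Φ(1.52 − 1.96), about 33%.

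**The case against.** A reader might infer that 4.1 turns every test into a confirmatory one. The documents do not support that. SAP 2.2.1.2 places formal hypothesis testing on the primary and four key secondary endpoints, 8.2 makes the other secondary analyses exploratory, and 8.1.1 and 8.1.2 both exclude subgroups from the gatekeeping. Specific sections normally qualify a general introduction. Protocol 13.1.4.6 also lists the antivenom-timing subsets under a heading that includes exploratory and sensitivity analyses, so one of the six factors has such a label, though only in the protocol.

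A reader might also take 65 significance tests as planned fact. In 8.1.2.1 to 8.1.2.4 the overall comparison is to be tested, whereas subgroup effects are to be estimated. That within-level P values will appear is an inference, although a reasonable one. SAP 4.1 says P values will be reported, the sample code in 8.1.3 for the continuous endpoints requests them through the pdiff option, and the table list in 13.2 gives the subgroup outputs the same statistical-analysis title as the main analyses. The number 65 is a maximum, and 8.2.2 reports unexpectedly few severely neurotoxic patients, so some strata may be thin.

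On size, the two-sided figures count results that favour placebo. The favourable ones are the relevant measure for a false claim of benefit.

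Finally, interaction tests do not cure everything. Subgroup confidence intervals would still show the discordance, and power is low. This objection stands. It limits what the remedy can achieve, but separate small-stratum results remain a worse basis for a claim of differential effect.

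**Conclusion.** The point holds as a defect of wording and method. SAP 4.1 leaves the scope of formal testing open, in conflict with 2.2.1.2 and 8.2. The SAP does not say how subgroup P values are to be read, and it plans separate models where a question about differential effect needs an interaction term.

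The further inference that a false subgroup claim is likely goes too far. What is fairly likely is a nominally significant result somewhere. A favourable one among all 65 is close to a coin toss, and a favourable primary-endpoint subgroup after a missed primary occurs in about one trial in six. Neither carries alpha in the fixed sequence. The near-certain problem is apparent heterogeneity when the effect is uniform (about 94%).

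All simulated figures rest on the assumed shares, independent factors and endpoint correlation. Country, snake type and neurotoxicity are plausibly related, which the simulation ignores. The fixed sequence for the five main hypotheses is not affected.

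**What to change.** 1. In SAP 4.1, state that only the primary endpoint and the four key secondary endpoints in the fixed sequence of 8.1.2 are confirmatory, and that all other analyses, including subgroup, sensitivity and other secondary analyses, are exploratory with nominal P values.
2. In SAP 8.1.1, 8.1.2.1 to 8.1.2.4 and 8.4, fit one model per subgroup factor in the full ITT population, with the planned covariates plus the factor and treatment-by-factor terms. Report the nominal interaction P value and the subgroup estimates with 95% confidence intervals. Base any statement of differential effect on the interaction, not on within-level significance, and state that interaction power is low (about 33% in the case worked above).
3. In SAP 8.4, correct three key secondary endpoints to four.

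The cost is SAP wording and six interaction models per endpoint (at most 6 × 5 = 30), with no new data and no change in sample size. The sponsor gives up the option of presenting a nominally significant subgroup as a formal result.
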